10 MEASUREMENT OF EFFECT

This is a feasibility study. Feasibility will be achieved if a treatment plan can be achieved with the parameters described below:

Specifically the treatment must fulfill all three aspects of a) coverage of the prostate PTV as defined in 5.3 to dose of 35 Gy in 5 fractions, b) no more than acceptable radiation dosage to organs at risk (OAR) by DVH analysis (refer to section 5.3), and c) full coverage of high-risk prostate nodules, as defined by mean dose to contoured nodules. The total mean dose to be delivered (either 37.5, 40, 42.5 or 45 Gy) will be determined by selecting the plan with the highest dose to visible nodules while maintaining normal tissue constraints. The first primary endpoint will be degree of feasibility, as measured by the percentage of treatments that are delivered according to plan.

Safety of this approach will be determined by assessing acute GI/GU toxicity (CTCAE 4.0 criteria). Treatment will be deemed safe if there are no acute greater than grade 3 GI/GU adverse events within the first 30 days of treatment (CTCAE 4.0 criteria). The second primary endpoint will be safety, as measured by the percentage of treatments that are delivered without GI/GU toxicity within the first 30 days from start of treatment. Given that the treatment plans will meet standard normal

tissue constraints used for SBRT, and rigorous safety metrics need to be met before radiation is delivered, we do not anticipate any increased toxicity on this study compared to standard SBRT.

11 DATA REPORTING / REGULATORY CONSIDERATIONS

11.1 Data Collection

The data collection plan for this study is to utilize REDCap to capture all treatment, toxicity, efficacy, and adverse event data for all enrolled patients.

11.2 REDCap

REDCap (Research Electronic Data Capture) is a free data management software system that is fully supported by the Weill-Cornell Medical Center CTSC. It is a tool for the creation of customized, secure data management systems that include Web-based data-entry forms, reporting tools, and a full array of security features including user and group based privileges, authentication using institution LDAP system, with a full audit trail of data manipulation and export procedures. REDCap is maintained on CTSC-owned servers that are backed up nightly and support encrypted (SSL-based) connections. Nationally, the software is developed, enhanced and supported through a multi-institutional consortium led by the Vanderbilt University CTSA.

11.3 Regulatory Considerations

All protocol amendments and consent form modifications will be made by the Principal Investigator.

11.4 Data Management

All patient data will be entered and maintained in REDCap. These data include clinical data and all patient safety data. The REDCap provides audit trails that track creation and modification of records that include user id and timestamp. Once entered, the data is subjected to validation procedures that are executed either immediately or upon saving the eCRF page or during the batch validation process. Validation failures that are identified before the page is saved can be corrected immediately. Validation failures during saving of the eCRF page and during batch validation processes will generate a discrepancy. Depending on the database account privileges, the data managers may be able to correct a discrepancy or if not, route it to the project data manager at WCMC who can take appropriate action to correct the problem. Data clarification forms can also be printed out when necessary to be sent to the project data manager at JCTO. Once the discrepancy is closed, by marking “resolved” or “irresolvable”, the data is marked clean and an audit trail is generated by the system.

All key end points will be source verified by a second person at each site and errors will be corrected. Once the data is verified and all discrepancies are closed, the data can be locked/frozen. Locking and freezing can be done at different granular levels and will follow institutional SOPs and any specific requirements for the project.

Security measures that will be taken in order to protect patient data will include firewall technology and database level security which will be achieved by assigning roles and privileges to different levels of users and by requiring that the users authenticate themselves using user id and password. Additional security for data transfer between remote clients and servers will be achieved by using digital certificates/SSL. All data will be backed-up to tape periodically according to the Institutional SOPs. All data will be stored for at least 5 years following the termination of this study.

12 STATISTICAL CONSIDERATIONS

12.1 *Study Design/Endpoints*

12.1.1 Primary Objectives

1. Determine the feasibility and safety of delivering SBRT w/SIB without increased acute G3 GI/GU toxicity.

Feasibility is defined as a plan fulfilling the treatment plan defined before the start of treatment. Specifically the treatment must fulfill all three aspects of a) coverage of the prostate PTV as defined in 5.3 to dose of 35 Gy in 5 fractions, b) no more than acceptable radiation dosage to organs at risk (OAR) by DVH analysis (refer to section 5.3), and c) full coverage of high-risk prostate nodules, as defined by mean dose to contoured nodules. The total mean dose to be delivered (either 37.5, 40, 42.5 or 45 Gy) will be determined by selecting the plan with the highest dose to visible nodules while maintaining normal tissue constraints. The first primary endpoint will be feasibility, as measured by the percentage of treatments that are delivered according to plan.

Safety of this approach will be determined by assessing acute GI/GU toxicity (CTCAE 4). The second primary endpoint will be safety, as measured by the percentage of treatments that are delivered without greater than grade 3 GI/GU toxicity within the first 30 days from start of treatment.

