1.1 Primary Objectives

1.1.1 Determine the feasibility and safety of delivering SBRT w/SIB without increased acute G3 GI/GU toxicity.

Feasibility is defined as a plan meeting treatment planning objectives and normal tissue constraints. Specifically the dose distribution of the MRI-guided technique, will be assessed with regard to fulfilling protocol requirements of: a) coverage of the planning target volume (PTV) , b) constraints to organs at risk (OAR) by dose volume histogram (DVH) analysis and whether this can be done through standard set-up techniques or non-invasively through MRI based planning, c) coverage of high-risk prostate nodules. The total dose delivered (either 37.5, 40, 42.5 or 45 Gy mean dose to the contoured nodule) will be determined by selecting the plan with the highest dose to visible nodules while maintaining normal tissue constraints to the urethra and rectum. We will track the number of treatment plans for each dose level (37.5, 40, 42.5 or 45 Gy) that can be delivered while planning objectives.

Safety of this approach will be determined by assessing acute GI/GU toxicity (CTCAE 4.0 criteria). Treatment will be deemed safe if there is no acute >G3 GI/GU toxicity within the first 30 days of treatment (CTCAE 4.0 criteria). Given that the treatment plans will meet standard normal tissue constraints used for prostate SBRT, we do not anticipate any increased toxicity on this study compared to standard prostate SBRT.

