5.3.2 Dose/Treatment Planning Parameters

The CTV (prostate +/- SV) will be treated to minimum mean dose of 35 Gy in 5 fractions. The prescribed dose to the CTV will be 7-7.25 Gy per fraction. There will be a simultaneous integrated boost to PIRADS 3-5 or PSMA avid nodules, delivering an additional 0.5, 1.0, 1.5 or 2 Gy per fraction for a total mean dose of 37.5, 40, 42.5 or 45 Gy to the contoured nodule. The highest mean radiation dose possible (37.5, 40, 42.5 or 45 Gy) that can be delivered while respecting normal tissue constraints to rectum and urethra will be selected.

Volume of the PTV receiving prescribed SBRT dose should be $\geq 95\%$; acceptable deviation is dose $>90\%$

Critical organ limits (SBRT monotherapy):

1. Rectum: Maximum dose to 1 cc 38.5 Gy, Max dose to 3 cc 34.4 Gy,, Max point dose 40 Gy. Acceptable deviation is maximum dose to 1 cc 39 Gy, max dose to 3 cc 36 Gy and max point dose of 42 Gy.
2. Bladder: Maximum dose to 1 cc 38.5 Gy, Max point dose 40 Gy. Acceptable deviation is max point dose of 42 Gy.
3. Penile Bulb: No more than 105% of prescription dose; D3cc 25 Gy. This is a soft constraint.
4. Femoral heads: Maximum point dose 30 Gy
5. Small bowel: Maximum point dose 25 Gy
6. Urethra: Max dose 40 Gy. Will allow up to 42 Gy.

5.4 *Supportive Care Guidelines*

- a. Urinary: A proportion of patients undergoing prostate SBRT can expect increase in urinary frequency or urgency. If this becomes bothersome to the patient, medication to alleviate symptoms can be prescribed at the discretion of the treating radiation oncologist and documented in patient chart.
- b. Bowel: Bowel symptoms during time of prostate SBRT can occur. If patients develop rectal urgency, tenesmus or diarrhea, medication to alleviate symptoms can be prescribed at the discretion of the treating radiation oncologist, and documented in patient chart.

5.5 *Duration of Therapy and Criteria for Removal from Study*

In the absence of treatment delays, the SBRT is anticipated to complete within 2-3 weeks time. Patients will undergo radiation 2-3 times a week, but treatment can be slowed down to once a week at the physician's discretion; these differing fractionation patterns fall within standard of care for SBRT. Patients can be removed from the study at any point should they decide they no longer wish to participate. They will continue to receive routine medical care as necessary outside the confines of this study.

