12.4 Analysis of Primary and Secondary Endpoints

Primary Endpoint:

The first primary endpoint of feasibility will be measured by the percentage of treatments that are delivered according to plan. The count and percent will be tabulated, and a 95% confidence interval estimated using an exact Clopper-Pearson binomial two-sided interval.

The second primary endpoint of safety will be measured by the percentage of treatments that do not lead to a GI/GU adverse event (defined as >Grade 3) within 30 days of treatment. The count and percent will be similarly tabulated, and a 95% confidence interval estimated using an exact Clopper-Pearson binomial two-sided interval.

Finally, the proportion of patients for whom the treatment was feasible and safe will be tabulated, and a 95% confidence interval estimated using an exact Clopper-Pearson binomial two-sided interval.

Planned sub-group analyses include feasibility, safety, and combination of both within each of the four potential target dose levels (37.5, 40, 42.5 or 45 Gy).

Secondary Endpoints:

HRQOL measures at baseline and at follow up (3-6 months post treatment start) will be summarized numerically and graphically using mean (sd), median (interquartile range), or count (percent) as appropriate, and 95% confidence intervals estimated where possible. Changes in scoring from pre- to post-treatment will also be similarly studied. EPIC overall scores as well as domain summary scores (urinary incontinence, urinary irritative/obstructive, bowel, sexual, hormonal) and individual item responses will be studied. Similarly, overall score as well as individual item responses will be studied for the AUA symptom survey.

13 Data and Safety Monitoring Plan (DSMP)

The WCMC Data and Safety Monitoring Committee (DSMC) is the central monitoring board for this study.

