13.2 Stopping rules

If patients experience more than one grade 4 or higher toxicity within one month of RT, the study will not proceed further.

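### The 30-day safety window runs from the first fraction while the pace is discretionary, so the post-treatment time it covers ranges from about 20-21 days down to 2

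*Combined protocol and SAP*

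**What the plan says.** **The window.** Two sections name an anchor for the second primary endpoint, and both name the start of treatment. Section 12.1.1 takes the percentage of treatments "delivered without greater than grade 3 GI/GU toxicity within the first 30 days from start of treatment". Section 10 takes the percentage "delivered without GI/GU toxicity within the first 30 days from start of treatment". (The two sentences also differ on grade, which is a separate matter.)

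The other places are looser:
- Section 1.1, like the Protocol Summary, calls treatment safe if there is "no acute >G3 GI/GU toxicity within the first 30 days of treatment".
- Section 12.4 counts treatments that "do not lead to a GI/GU adverse event (defined as >Grade 3) within 30 days of treatment".
- The stopping rule in section 13.2 refers to "more than one grade 4 or higher toxicity within one month of RT".

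None of these places the anchor at the end of treatment.

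**The pace.** By section 5.3.2 the CTV is "treated to minimum mean dose of 35 Gy in 5 fractions". Section 5.5 gives the fractions two or three times a week and expects the course to finish in 2-3 weeks if there are no delays. It adds that "treatment can be slowed down to once a week at the physician's discretion". No section adjusts the safety window for a slowed course.

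**Data collection.** The section 5 calendar schedules CTCAE grading before treatment, at fraction 5, and at the visit 3-6 months after RT. Section 7.2 has all adverse events entered on a patient-specific log.

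**The concern.** A window of fixed length from the first fraction covers the course itself plus whatever time remains. When the pace is left to the physician, that remainder is set by the schedule and not by the endpoint definition. After a weekly course almost none remains. A qualifying GI/GU event that begins two weeks after the last weekly fraction is scored as no toxicity in the primary safety endpoint. The same event two weeks after a course at two or three per week is counted.

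This matters because sections 1.1 and 10 make the safety conclusion depend on there being no qualifying event. With 30 patients, one event on the wrong side of the boundary changes the conclusion. Section 12.4 also pools all patients into one proportion and repeats it within four dose levels, without reporting pace.

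**Working it through.** **Inputs.** Window: 30 days from start (sections 10 and 12.1.1). Fractions: 5 (section 5.3.2). Pace: 2-3 per week, or weekly (section 5.5). The first fraction is day 0.

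**Formula.** Days left after the last fraction = 30 - (day of fraction 5).

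**The plan's own figure.** With at least one day between fractions and weekdays only, three per week puts fraction 5 on day 9 (0, 2, 4, 7, 9) or day 10 (0, 3, 5, 7, 10). Two per week always gives day 14 (for example 0, 3, 7, 10, 14). Counted in calendar weeks, these courses end in the second or third week, which agrees with the 2-3 weeks in section 5.5.

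| Pace | Fraction 5 | Days left now | Close of window if it ran to 30 days after fraction 5 |
|---|---|---|---|
| 3 per week | day 9-10 | 30 - 9 = 21; 30 - 10 = 20 | day 39-40 |
| 2 per week | day 14 | 30 - 14 = 16 | day 44 |
| weekly | day 28 | 30 - 28 = 2 | day 58 |

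**Sensitivity.**
- If 2-3 weeks means 14-21 elapsed days, the usual pace leaves 30 - 21 = 9 to 30 - 14 = 16 days.
- If the first fraction is day 1 and the window ends on day 30, each figure falls by one; weekly leaves 1 day.
- If a course is slowed part-way, with the remaining gaps at 3.5 days: one weekly gap gives 7 + 3 × 3.5 = 17.5, leaving 12.5 days; two give 14 + 2 × 3.5 = 21, leaving 9; three give 21 + 3.5 = 24.5, leaving 5.5.

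**Direction.** The current window is day 0 to 30. The alternative is day 0 to (day of fraction 5 + 30), which contains it. Every patient with an event under the current window also has one under the alternative, so the current safety rate is equal or higher. No assumption about onset is needed.

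**Size.** The difference equals the share of patients whose only qualifying events begin after day 30 and within 30 days of fraction 5. The documents give neither the share slowed nor the onset times, so it cannot be calculated. As a scale only: one such patient in 30 moves the rate by 1/30 = 3.3 points. It takes 30/30 (exact 95% interval 88.4% to 100%) to 29/30 = 96.7% (82.8% to 99.9%), and the no-event criterion is then not met.

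**The case against.** **Equal total time.** A fixed window from the first fraction gives every patient the same 30 days. A reader might infer that patients are pooled over unequal risk periods. That is not so: only the split between on-treatment and post-treatment time differs. The alternative makes total length vary, from about 39 to 58 days. Each anchor equalises one quantity and not the other. This stands, and is a real cost of the change.

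**Events on treatment count.** A reader might infer that acute toxicity in weekly patients goes uncounted. Anything that begins by day 30 counts, including the whole 28-day course. A reader might also take 2 days out of 30 as the share of toxicity captured. That would start the onset clock at the last fraction and ignore the first four. On the day grids 0, 7, 14, 21, 28 (weekly), 0, 3, 7, 10, 14 and 0, 2, 4, 7, 9, the mean time in the window after each fraction is 16, 23.2 and 25.6 days, a milder contrast. The documents give no onset distribution, so no capture percentage is supported.

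**Symptom-driven slowing.** A reader might infer that the patients with most toxicity are slowed and so watched least. Section 5.5 says only that pace is at the physician's discretion. Symptoms that did prompt slowing would have arisen on treatment, inside the window.

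**Ascertainment.** The 2, 16 and 20-21 days are nominal. By the calendar, no patient has a scheduled CTCAE assessment between fraction 5 and 3-6 months. Section 12.1.2 still puts the first follow-up at about one month for quality of life, which conflicts with the calendar and with sections 1.2 and 5.6. Scheduled grading at fraction 5 even falls later in the window for weekly patients (day 28). Moving the anchor does not by itself improve ascertainment.

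**Small practical effect.** Section 2.6 describes the whole-prostate dose as free of acute grade 3 toxicity in the literature, and events above grade 3 should be few. Later events still reach the AE log and the 3-6 month assessment. This limits the likely size, but a no-event criterion is sensitive to a single case.

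**Unsettled anchor.** Section 12.4 names no anchor. That is true, and it is a further reason to state one. The only two sections that name one choose the start.

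**Conclusion.** The concern holds in a limited form. With the anchor in sections 10 and 12.1.1 and the pace allowed in section 5.5, nominal post-treatment time in the primary safety window is about 20-21, 16 or 2 days. It is 9-16 days at the usual pace if 2-3 weeks is read as elapsed time. The day counts assume no delays and a first fraction on day 0. Events that begin after day 30 fall outside this endpoint, though not outside the trial's records. The reported safety rate is equal to or higher than one covering 30 days after the last fraction. That direction follows from the definitions; the size is unknown.

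It would go too far to say that the rate has been shown to be biased towards 100%. The difference could be zero, and would be if no qualifying event began after day 30. The point is an inexpensive improvement to a primary endpoint and does not invalidate the design.

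**What to change.** In sections 1.1, 10, 12.1.1 and 12.4, and in the matching text of the Protocol Summary, use one window for every patient: from the first fraction through 30 days after the last SBRT fraction. Assign events by onset date, taken from the AE log and the 3-6 month CTCAE visit, and make onset date a required field. Keep the 30-days-from-start count as a supportive figure, and tabulate the number of patients by fraction pace. The anchor of the stopping-rule period in section 13.2 should also be stated so that it can be read alongside the endpoint; no rule is proposed here. The permitted treatment schedule stays as it is.

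Costs:
- Rewording in a few places and one data field.
- A safety rate that may be slightly less favourable.
- A total window that varies with pace, from about 39 to 58 days, which the pace table makes visible.
- Reliance on the AE log and recalled onset dates for late events, because no CTCAE visit is scheduled between fraction 5 and 3-6 months. The report should say so.

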2.6 ViewRay: a unique radiation delivery approach

The ViewRay MRIdian Linac system is a radiation delivery machine that integrates a linear accelerator with real-time MRI imaging. The ViewRay machine allows fusion of MR imaging with treatment planning. The uniqueness of this approach is the image guided delivery component, based on precise MRI-based detection of target and normal tissue during treatment in real-time. The ViewRay will provide real-time MRI imaging to ensure that the high-dose region is precisely targeted. MRI guided radiation has the benefit of not requiring fiducial implantation or excess radiation exposure from multiple cone beam CT. Furthermore, motion monitoring can be

performed with images acquired up to 4 frames a second, allowing live feedback of treatment position.

ViewRay offers the ideal system for delivery of prostate SBRT, due to its ability to provide image guidance “live”, during treatment. Real-time MRI imaging allows superior soft-tissue differentiation with excellent visualization of the prostate. This ViewRay platform offers the ideal setting for this study, that aims at precisely delivering prostate SBRT with a simultaneous integrated boost to visible nodules.

The goal of this study is to assess feasibility and safety of using the ViewRay to deliver prostate SBRT with SIB. Feasibility is defined as the ability to deliver treatment as planned (within the constraints defined in Section 5.3 Radiation Planning) and safety is defined as lack of acute G3 GI or GU toxicity within 30 days. The proposed SBRT dose (35-36.25 Gy in 5 fractions to the whole prostate) has been reported in the literature to be safe and well tolerated (Table 2), with no acute G3 toxicity. The proposed boost dose of an additional 0.5, 1.0, 1.5 or 2 Gy per fraction (total dose 37.5-45 Gy, depending on normal tissue constraints) is within the range of current standard of care SBRT doses, and is expected to be well-tolerated if normal tissue constraints are met. By applying rigorous normal tissue constraints and capitalizing on the imaging capability of the ViewRay we plan to deliver a treatment that is non-invasive and exceptionally precise.

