5 STUDY PROCEDURES

| | Pre-Study | Fx 1 | Fx2 | Fx 3 | Fx 4 | Fx 5* | Post-RT Visit (3-6 month s/p RT) |
|--|-----------|------|-----|------|------|-------|----------------------------------|
| Informed consent | X | | | | | | |
| Demographics | X | | | | | | |
| PSA | X | | | | | | X |
| Acute/Late Toxicity Assessment (CTCAE) | X | | | | | X | X |
| EPIC-26, AUA | X | | | | | | X |
| Imaging: Planning CT/MR; | X | | | | | | |
| Optional: blood draw and microbiome sample | X | | | | | X | X |

**at physician's discretion, lymph nodes may be targeted in the radiation field, either in 5 fractions or over 5-6 weeks using standard fractionation*

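### At 2-3 fractions a week, no CTCAE grading is scheduled in the last 15-20 days of the 30-day primary safety window, and the sections disagree on whether grade 3 counts

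*Combined protocol and SAP*

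**What the plan says.** **Endpoint and window.** Section 12.1.1 counts treatments delivered "without greater than grade 3 GI/GU toxicity within the first 30 days from start of treatment". Section 10 uses the same anchor but gives no grade in its endpoint sentence: "delivered without GI/GU toxicity within the first 30 days from start of treatment". Section 1.1.1, like the Protocol Summary, gives the decision rule: "Treatment will be deemed safe if there is no acute >G3 GI/GU toxicity within the first 30 days of treatment". The analysis text in 12.4 counts events "defined as >Grade 3) within 30 days of treatment". The background in 2.6 says that "safety is defined as lack of acute G3 GI or GU toxicity within 30 days".

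**Assessments.** In the section 5 table, the row "Acute/Late Toxicity Assessment (CTCAE" is marked at pre-study, fraction 5 and the post-RT visit 3-6 months after radiation, and nowhere else. Section 5.6 gives the same 3-6 months.

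**Pace of treatment.** Section 5.5 gives 2-3 sessions a week, which may be slowed to weekly, and says that "the SBRT is anticipated to complete within 2-3 weeks time".

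**Unscheduled capture.** Sections 7 to 7.4.1 provide for events reported by patients or observed by staff, an AE log, CTCAE grading of grade 3 or higher, SAE reporting, and follow-up until resolution or stabilisation.

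**Quality of life.** Section 12.1.2 places first follow-up about one month after treatment ends. Sections 1.2.1 and 5.6 and the schedule place it 3-6 months after radiation. Section 12.4 counts the 3-6 months from the start of treatment.

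**The concern.** A primary endpoint fixed at 30 days needs a planned look at or near day 30. Here the last planned look is at the final fraction, and the next comes months after the window has closed. For the time between fraction 5 and day 30, a patient would be counted as event-free because nobody reported an event, not because someone checked.

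The decision rule tolerates no qualifying event, so a single event that is missed, or placed on the wrong side of day 30, changes the conclusion. The grade wording also decides which events are looked for. Read literally, >G3 leaves grade 3 out, while the objective and 2.6 are framed around G3.

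**Working it through.** **1. The plan's own interval.** Section 12.2 gives an exact Clopper-Pearson 95% interval of 31.3% to 68.7% for a 50% rate with 30 patients. For 15/30 the beta quantiles give 31.3% to 68.7%, so it reproduces. (The ±16% printed beside it is a separate matter and is not used here.)

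**2. Days without scheduled grading.** Inputs: five fractions (Protocol Summary), 1-3 per week (5.5), CTCAE at fraction 5 and then 3-6 months after radiation (section 5). Fraction 1 is day 1. Ungraded days = 30 − day of fraction 5. Earliest next grading = day of fraction 5 + 91 (three months).

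| Pace | Fraction days | Ungraded days | Share of window | Earliest next grading |
|---|---|---|---|---|
| 3 per week | 1, 3, 5, 8, 10 | 30 − 10 = 20 | 67% | day 101 |
| 2 per week | 1, 4, 8, 11, 15 | 30 − 15 = 15 | 50% | day 106 |
| 1 per week | 1, 8, 15, 22, 29 | 30 − 29 = 1 | 3% | day 120 |

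A Friday start at three per week puts fraction 5 on day 11 and leaves 19 days. If the anticipated 2-3 weeks is read as elapsed time, fraction 5 falls on day 14-21 and the gap is 30 − 14 = 16 to 30 − 21 = 9 days. The earliest next grading, day 101, is 101 − 30 = 71 days after the window closes.

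**3. What one event is worth.** The exact 95% upper limit for 0/30 is 1 − 0.025^(1/30) = 11.6%. For 1/30 it is the 97.5% quantile of Beta(2, 29) = 17.2%. As the percentage without an event, which is how 12.4 reports it, the lower limit moves from 88.4% to 82.8%.

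**4. Grade and anchor side by side.**

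| Place | Grade | Start of the window |
|---|---|---|
| Objective sentence, 1.1.1 and 12.1.1 | no increase in acute G3 | not stated |
| Decision rule, Summary, 1.1.1 and 10 | above G3 | opening 30 days of treatment |
| 2.6 | G3 | not stated |
| Endpoint sentence, 10 | none | start of treatment |
| Endpoint sentence, 12.1.1 | above grade 3 | start of treatment |
| Analysis, 12.4 | above grade 3 | could be start or end |
| Stopping rule, 13.2 | 4 or higher | one month, relative to RT, no anchor |

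The real grade conflict is between G3 (objective, 2.6) and above G3 (decision rule, endpoint, analysis). The anchor is settled in 10 and 12.1.1 and loose in 12.4 and 2.6.

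**5. Does the one-month follow-up in 12.1.2 close the gap?** No. It concerns quality of life, not CTCAE, and it contradicts 1.2.1, 5.6 and the schedule. At 2-3 fractions a week it would fall on day 10 + 30 = 40 to day 15 + 30 = 45, after the window has closed.

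**The case against.** The strongest reply is that the endpoint as worded concerns grade 4-5 events, which do not wait for a clinic visit. Such events would ordinarily meet the SAE definition in 7.3 and 7.4. Patients report them, staff log them, and they are followed to resolution. Much of this stands: a reader might infer that primary safety events will go uncounted, and the documents do not show that. The reply is weaker if grade 3 is meant to count, since such events are less likely to surface unprompted. In either case, nothing in section 7 sets a contact between fraction 5 and month 3.

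Four other readings go too far:

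- **The anchor conflicts throughout.** Counting the first 30 days of treatment naturally means from the start, which agrees with 10 and 12.1.1.
- **Section 10 counts toxicity of any grade.** The sentence just before its endpoint sentence says greater than grade 3.
- **Onset dates are not collected.** The protocol does not mention them, but that is case-report-form detail and the forms are not in the documents. Section 11.4 also requires second-person source verification of key endpoints.
- **Nodal patients are still being irradiated when the window closes.** The footnote says "lymph nodes may be targeted in the radiation field, either in 5 fractions or over 5-6 weeks using standard fractionation" but gives no sequence relative to the five fractions, so no day count can be drawn from it.

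It is also fair to say that 15-20 days is the wider range. The elapsed-time reading gives 9-16 days, and the permitted weekly pace leaves about 1.

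**Conclusion.** The concern holds as an assessment gap and a wording conflict. At 2-3 fractions a week, half to two thirds of the primary safety window has no scheduled grading, and the first planned look afterwards is at least 71 days too late. This rests on fraction 1 as day 1, weekday treatment and no delays.

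The effect on the result cannot be sized from the documents, because they give no rate at which unscheduled reporting captures events. If no qualifying event occurs, there is no effect. If exactly one occurs and is missed, the verdict of safe is wrong and the upper limit is reported as 11.6% when it should be 17.2%.

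The grade conflict is independent of the gap, and the documents do not resolve it. The quality-of-life timing is a separate, smaller inconsistency. The version 2.0 summary of changes records the move from one month to 3-6 months, so 12.1.2 is probably text left unrevised.

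**What to change.** 1. Add to the section 5 schedule one brief remote CTCAE GI/GU assessment at about day 30 from fraction 1, with onset dates recorded.
2. Reconcile the grade threshold across the objective sentence (1.1.1, 12.1.1), 2.6, 10, 12.1.1 and 12.4, and state it in section 10's endpoint sentence. Which grade is intended is for the investigators to say.
3. Carry the start-of-treatment anchor of 10 and 12.1.1 into 12.4 and 2.6, and reconcile the unanchored window in 13.2 with it.
4. In 12.1.2 and 12.4, give the quality-of-life follow-up as 3-6 months after completion of radiation, as in 1.2.1, 5.6 and the schedule.

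The cost is a short amendment and one short contact per patient, 30 in all. The reported toxicity rate may rise slightly because events are actively sought. The sample size and the planned intervals do not change.
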